Randomised Controlled Trial for investigation of the timing to allow weight bearing walking after soft tissue hallux valgus correction

Affiliations

Department of Orthopaedics and Traumatology, North District Hospital, Sheung Shui, Hong Kong.

Abstract

Many patients with Hallux Valgus feel that the restriction of weight bearing immediately after surgery an obstacle to their activities of daily living and one of the chief determining factors to undergo surgery or not. There has been no trial to investigate the optimal timing to allow weight bearing walking after distal soft tissue reconstruction for hallux valgus. The objective of the randomized controlled trial is to investigate whether early partial weight bearing will improve the outcomes of patients undergoing Endoscopic Assisted Distal Soft Tissue Procedure (EDSTP).

This is an open-label randomized controlled trial. Fifty adult (>18 yrs) patients who undergo hallux valgus by the EDSTP will be recruited and randomly assigned to trial group and control group. Subjects in the control group follow the existing rehabilitation protocol of non-weight bearing walking for 6 weeks followed by heel walking for 6 weeks, followed by the resumption of normal full weight-bearing walking in normal shoes at 12 weeks post-operation. Subjects in the trial group begin heel walking when the bulky dressing and sutures are removed at 2 weeks post-operation and resume full weight bearing walking in normal shoes at 12 weeks post-operation. The primary outcome is radiological changes including hallux valgus angle (HVA), intermetatarsal angle (IMA), and tibial sesamoid position by weight bearing feet X-Rays at 12, 18, and 26 weeks post-surgery. Other outcomes include pain, range of motion, and foot function.

Introduction

Although Hallux Valgus is a common problem presenting to the foot and ankle surgeon, many aspects of this disease entity are still poorly understood. Surgical procedures are plenty, and can be very broadly classified into those that correct the deformity via soft tissue reconstruction and those that correct through osteotomies. There is currently no gold standard surgical procedure that is proven to be the most superior and lots of exciting research is being undertaken globally. The commonest distal soft tissue procedure is the McBride operation where the tight lateral tissues such as the adductor hallucis and lateral capsule are released while the lax medial capsule is plicated and a bunionectomy is performed. Upon this theoretical background, multiple modifications of the original procedure have been proposed, from double skin incisions to endoscopic variants.

Many patients feel that the restriction of weight bearing immediately after surgery an obstacle to their activities of daily living (ADL) and one of the chief determining factors to undergo surgery or not. Rehabilitation plans vary even amongst pure distal soft-tissue procedures, with some units allowing immediate post-operative weight bearing, while others having a 12-week

period of post-operative non-weight bearing walking. Not critical evidence is available to account for the discrepancies but a prolonged period of non-weight bearing is usually employed in the fear that the construct will fail and early recurrence will occur if stressed too early.

To the best of our knowledge, there has been no trial to investigate the optimal timing to allow weight bearing walking after distal soft tissue reconstruction for hallux valgus. This article will investigate if early weight bearing will affect the outcomes for patients whom have underwent Endoscopic Assisted Distal Soft Tissue Procedure (EDSTP). This procedure is chosen because the it is a minimally invasive modification of the McBride procedure and has one of the longest publishing track records. It is the default procedure of choice in the investigators' institution; with the current post-operative protocol requiring the patient to undergo a 6-week period of non-weight bearing walking before initiating heel walking at 6 weeks.

Hypothesis and study objectives

The objective of the randomized controlled trial is to investigate whether early partial weight bearing will improve the outcomes of patients undergoing EDSTP.

We hypothesize that compared with standard 6-week non-weight bearing, early partial weight bearing walking at 2 weeks post-surgery improves the patient's quality of life, allows faster rehabilitation with better 1MTPJ range of motion and faster decrease in generalized swelling. This early weight bearing rehabilitation program will not negatively affect the stability of the surgical reconstruction correction and maintains a good radiological outcome as well as the traditional rehabilitation protocol where weight bearing begins at 6 weeks.

Patients and Methods

Patients

This is an open-label randomized controlled trial. We aim to recruit 50 adult (>18 yrs) patients who undergo hallux valgus by the EDSTP will be recruited. Exclusion criteria are those whom have disabilities (both physical and mental) which may impair the adherence of the rehabilitation and those who have undergone additional procedures such as concomitant 2nd toe deformity correction.

Randomization will be performed after the end of the EDSTP surgery to ensure there is no bias during the surgical procedure. Parallel groups will be allocated at 1:1 ratio via a computer generated random number, with 25 patients at each group.

In the control group, the subjects will follow the existing rehabilitation protocol of non-weight bearing walking for 6 weeks followed by heel walking for 6 weeks, followed by the resumption of normal full weight-bearing walking in normal shoes at 12 weeks post-operation. In the trial group, the subjects will begin heel walking when the bulky dressing and sutures are removed at 2 weeks post-operation and resume full weight bearing walking in normal shoes at 12 weeks post-operation. All subjects will be followed-up at 2 weeks, 6 weeks, 12 weeks, 18 weeks and 26 weeks post-operatively.

This study will be performed in the North District Hospital in Hong Kong. The study protocol will be approved by the Joint Chinese University of Hong Kong – North Territories East Cluster Clinical Research Ethics Committee and all participant will provide written informed consent. The study procedure will be conducted in compliance with Declaration of Helsinki and Good Clinical Practice (GCP) Guidelines.

Study outcomes

The primary outcomes are:

- Radiological changes including hallux valgus angle (HVA), intermetatarsal angle (IMA), and tibial sesamoid position by weight bearing feet X-Rays will be measured at 12, 18, and 26 weeks post-surgery.

Secondary Outcomes are:

- Pain at the bunion, the first metatarsophalangeal joint (1MTPJ) and transfer metatarsalgia using the visual analogue scale will be measured at 2, 6, 12, 18, and 26 weeks post-surgery.
- Range of Motion (ROM) at 1MTPJ will be measured at 2, 6, 12, 18, and 26 weeks post-surgery.
- Foot function measured by the American Orthopaedic Foot and Ankle, Score hallux score, which ranges from 0 to 100, will be conducted at 12, 18, and 26 weeks post-surgery.
- Foot function by the self-reported Foot and Ankle Outcome Score (FAOS) questionnaire will be measured at 12, 18, and 26 weeks post-surgery. FAOS consists of 5 subscales: pain, other Symptoms, function in ADL, function in sport and recreation, and foot and ankle-related Quality of Life. The previous week is taken into consideration when answering the questionnaire. Standardized answer options are given (% Likert boxes) and each question gets a score from 0 to 4. A normalized score (100 indicating no symptoms and 0 indicating extreme symptoms) is calculated for each subscale.

Statistical analysis

All analyses will be performed in IBM SPSS Statistics, Version 20.0 (SPSS Inc, Chicago, IL, USA). Results are shown as mean \pm SD, median (interquartile range) or number (frequency) depending on the type and distribution of data. Between-group comparisons will be conducted by one-way analysis of variance (continuous normal distributed data), Mann-Whitney U test (continuous non-normally distributed data), or chi-square test (categorical data) depending on the type and distribution of data. All hypotheses are two-tailed, and p values <0.05 are considered statistically significant.

References

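### The X-ray hypothesis is that early walking is no worse than standard, but the plan has only two-tailed difference tests, with no margin and no between-group confidence interval

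*Combined protocol and SAP*

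**What the plan says.** The general aim is worded as improvement. Under Hypothesis and study objectives the protocol states: "The objective of the randomized controlled trial is to investigate whether early partial weight bearing will improve the outcomes of patients undergoing EDSTP". The Abstract says the same.

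The hypothesis that follows has two parts. Quality of life, range of motion and swelling are expected to be better with early walking. The radiological prediction differs: "This early weight bearing rehabilitation program will not negatively affect the stability of the surgical reconstruction correction and maintains a good radiological outcome". The comparator is explicit, since early walking "maintains a good radiological outcome as well as the traditional rehabilitation protocol".

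The Abstract defines the primary outcome: "The primary outcome is radiological changes including hallux valgus angle (HVA), intermetatarsal angle (IMA), and tibial sesamoid position by weight bearing feet X-Rays". Study outcomes lists the same three measures at 12, 18 and 26 weeks. They are the only radiological measures in the protocol.

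The Statistical analysis section is one paragraph. Results are summarised by group as mean ± SD, "median (interquartile range) or number (frequency) depending on the type and distribution of data". For testing, "Between-group comparisons will be conducted by one-way analysis of variance (continuous normal distributed data), Mann-Whitney U test" or chi-square is used according to data type, with every hypothesis two-tailed at 0.05. The documents give no margin, no non-inferiority or equivalence test, no between-group confidence interval and no sample size calculation.

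**The concern.** A difference test can show that early walking is worse. A significant improvement would also imply that it is not worse. If the arms are truly similar, which is what the radiological hypothesis predicts, the expected result is p≥0.05, and the plan attaches no conclusion to that result. It has no rule to separate a finding of no worse from a trial too imprecise to tell.

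This matters because the Introduction attributes long non-weight bearing to worry that early loading will undo the repair and bring the deformity back. Whether early walking costs any correction is therefore central to a change of practice, and it is the question this analysis cannot settle in the expected case.

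**Working it through.** **Inputs.** From the documents: 25 per arm, 1:1 allocation, two-tailed 0.05, three measures at three visits. Not given: SD, effect size, power, margin, dropout. Results are therefore in SD units, and the effects and margins are illustrative. The planned 50 patients come without a calculation, so there is no figure to reproduce.

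**1. Precision, one continuous measure at one visit.** Half-width of the 95% CI = t(0.975, 2n−2) × √(2/n).
- 25 per arm: 2.011 × √(2/25) = 2.011 × 0.283 = 0.569 SD.
- 20 per arm (an assumed 20% loss): 0.640 SD.

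**2. How often p≥0.05 occurs.** Noncentral t, 48 df, noncentrality d/√(2/25).

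| True worsening | 25 per arm | 20 per arm |
|---|---|---|
| 0 | 0.950 | 0.950 |
| 0.3 SD | 0.820 | 0.848 |
| 0.5 SD | 0.590 | 0.662 |
| 0.6 SD | 0.453 | 0.544 |

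At 25 per arm, a non-significant result is 0.950/0.820 = 1.16 times as likely under no difference as under a 0.3 SD worsening, and 0.950/0.590 = 1.61 times as likely as under 0.5 SD.

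**3. All nine tests together.** Simulation of nine t-tests, 40,000 trials per setting, assuming correlations of 0.8 or 0.9 between visits and 0.3 to 0.7 between measures, with the same shift on every measure and visit. All nine are non-significant in:
- 74–82% of trials with no difference;
- 43–58% at 0.3 SD worse;
- 14–29% at 0.5 SD worse.

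Pairing the low ends and the high ends of these ranges, a wholly null set is about 1.4 to 1.7 times as likely under no difference as under 0.3 SD (0.822/0.576; 0.742/0.425), and about 3 to 5 times as likely as under 0.5 SD (0.822/0.287; 0.742/0.141).

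**4. Chance of concluding no worse when the arms are equal.** The planned test can do this only through a significant improvement, which arises by chance in 2.5% of trials. If instead the upper 95% limit must lie below a margin M, the probability at 25 per arm is 0.410 for M = 0.5 SD, 0.547 for 0.6 SD and 0.791 for 0.8 SD. It reaches 80% at M = 0.809 SD (0.909 SD with 20 per arm).

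**5. Patients per arm for 80% power, true difference zero.** 64 for M = 0.5 SD, 45 for 0.6, 34 for 0.7 and 26 for 0.8. A normal approximation, 2(1.960 + 0.842)²/M², gives 63 and 44 for the first two and a smallest margin of 0.79 SD at 25 per arm, which agrees closely.

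**6. A three-way conclusion rule.** 400,000 simulated trials, 25 per arm:

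| M | True worsening | Worsening shown | No worse | Inconclusive |
|---|---|---|---|---|
| 0.5 SD | 0 | 0.025 | 0.408 | 0.567 |
| 0.5 SD | 0.5 SD | 0.410 | 0.025 | 0.564 |
| 0.6 SD | 0 | 0.025 | 0.547 | 0.428 |
| 0.81 SD | 0 | 0.025 | 0.801 | 0.174 |
| 0.81 SD | 0.81 SD | 0.801 | 0.025 | 0.173 |

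A lower limit above 0 together with an upper limit below M occurs in about 0.01% of trials or fewer for M up to 0.81 SD.

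**The case against.** The strongest reply is that this is a superiority or direction-neutral trial. The stated objective is improvement, the Introduction also words the aim neutrally, and two-tailed tests suit both. The protocol never uses the language of non-inferiority and does not formally tie the radiological hypothesis to the endpoint list. This is fair for the general aim. It does not remove the explicit comparative sentence about radiology, which concerns exactly what the primary outcomes measure.

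Second, the plan never says that p≥0.05 will be read as no loss of correction, and a reader could compute a confidence interval from the reported means and SDs. Both are true. What remains missing is a pre-set margin and a conclusion rule; a margin chosen after the results are known would carry little weight.

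Third, the single-test figures are the least favourable view. This stands in part: nine null results are fair evidence against a uniform 0.5 SD worsening, though weak against 0.3 SD.

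Fourth, naming one measure and visit narrows the primary outcome, and analysing a post-operative value is not the same as analysing change. A margin for each measure would also answer the concern. Randomisation makes the expected between-arm difference the same for the value as for change from a pre-randomisation film, but the choice should be stated openly.

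**Conclusion.** The concern holds, and the plan should be changed before data are examined. As written, the analysis of the primary outcomes cannot confirm the hypothesis about them in the situation that hypothesis predicts. With 25 per arm, one measure and one visit, a non-significant result leaves a 95% CI of ±0.57 SD and would occur in 59% of trials even with a 0.5 SD worsening.

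The text comparison needs no assumptions. The sizes rest on t-tests of approximately normal data, on illustrative effects and margins in SD units, and, for the nine-test figures, on assumed correlations and a uniform shift. Nothing is claimed in degrees, and the t-test figures may not apply to sesamoid position if it is graded. The difference tests remain suitable for the outcomes expected to improve.

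**What to change.** Before data are examined:

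1. State that the radiological hypothesis is non-inferiority and that range of motion, quality of life and similar outcomes are superiority. Reconcile the improvement objective in the Abstract and in Hypothesis and study objectives with this.
2. Name one continuous radiological measure and one scheduled visit (for example the HVA value at 26 weeks). Have the sponsor set and justify a largest acceptable worsening, M.
3. Report the two-sided 95% CI for trial minus control, with higher meaning worse, and conclude in this order:
   - lower limit above 0: worsening shown (also say whether the upper limit is below M);
   - otherwise, upper limit below M: no worse than the standard protocol by M (add that improvement is shown if the upper limit is below 0);
   - otherwise: inconclusive.

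   Do not call the second result maintained correction, because both arms could lose correction equally. Describe the absolute part of the hypothesis from each arm's own values.
4. State that p≥0.05 is not evidence of no loss of correction. Report the other radiological measures and visits with 95% CIs as supportive.
5. State that 25 per arm gives 80% power only for a margin of about 0.81 SD if the true difference is zero.

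**Cost.** Text changes plus the sponsor's justification of M. No new films are needed if post-operative values at 12, 18 or 26 weeks are analysed; analysing change would need a baseline film that the documents do not list. Fifty patients suffice for 80% power only if M is about 0.81 SD or wider (0.91 SD with 20 evaluable per arm). A margin of 0.6 SD needs 2 × 45 = 90 patients and 0.5 SD needs 2 × 64 = 128. If the trial stays at 50 and the arms are equal, an inconclusive result is likely with a tighter margin: about 57% at 0.5 SD and 43% at 0.6 SD.

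### Allocation follows surgery but the arms are described as differing only from the 2-week visit, so week-2 pain and ROM cannot show a regimen effect and would serve better as a concealed pre-divergence baseline

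*Combined protocol and SAP*

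**What the plan says.** On timing, the Patients subsection of Patients and Methods states: "Randomization will be performed after the end of the EDSTP surgery to ensure there is no bias during the surgical procedure". It gives no interval between the end of surgery and allocation, and does not say when patients or staff learn the result. The trial is open-label.

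On the regimens, the control group has "non-weight bearing walking for 6 weeks followed by heel walking for 6 weeks". In the trial group, "the subjects will begin heel walking when the bulky dressing and sutures are removed at 2 weeks post-operation". Both groups return to full weight bearing at 12 weeks.

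On measurement, "All subjects will be followed-up at 2 weeks, 6 weeks, 12 weeks, 18 weeks and 26 weeks post-operatively". Under Study outcomes, pain at the bunion, at the first metatarsophalangeal joint (1MTPJ) and as transfer metatarsalgia is assessed "using the visual analogue scale will be measured at 2, 6, 12, 18, and 26 weeks post-surgery". Also, "Range of Motion (ROM) at 1MTPJ will be measured at 2, 6, 12, 18, and 26 weeks post-surgery". No pre-operative measurement of either is scheduled.

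On analysis, the Statistical analysis section gives one general rule: "Between-group comparisons will be conducted by one-way analysis of variance (continuous normal distributed data), Mann-Whitney U test (continuous non-normally distributed data", with chi-square for categorical data, two-sided at 0.05. It names no baseline value or covariate and does not treat week 2 differently from later visits.

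**The concern.** A randomised comparison of two regimens tells us about the regimens only once they differ. Here the described difference starts at the 2-week visit, yet the week-2 values stand in the same outcome list, under the same tests, as weeks 6 to 26. Three things are at stake.

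- **Misreading.** A significant week-2 difference in pain or ROM could be reported as an early benefit. The stated hypothesis claims better 1MTPJ motion and faster rehabilitation, so such a result would fit the expected story.
- **Open allocation.** If patients and staff know the allocation before week 2, behaviour and pain reports may shift before any difference in regimen. Losses in that period would also count as post-randomisation losses. The documents give no figure for such losses.
- **A wasted measurement.** Week 2 is the only scheduled pain and ROM assessment before the arms diverge. The planned tests at weeks 6 to 26 do not use it.

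**Working it through.** **Inputs from the documents.** 25 patients per arm; two-sided 0.05; pain at 3 sites and ROM at weeks 2, 6, 12, 18 and 26; unadjusted between-group tests.

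**Assumed.** The correlation between the week-2 value and a later value of the same measure, and the correlation among the week-2 measures. The documents give neither.

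**The plan's own figure.** 25 + 25 = 50 agrees with the stated total. Nothing more can be reproduced, because no effect size, SD, power or dropout is given.

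**Step 1: where the arms differ.**

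| Period | Control | Trial group |
|---|---|---|
| Weeks 0–2 | non-weight bearing | no weight bearing described; heel walking starts at week 2 |
| Weeks 2–6 | non-weight bearing | heel walking |
| Weeks 6–12 | heel walking | heel walking |
| From week 12 | full weight bearing | full weight bearing |

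The described contrast lies in weeks 2 to 6. The week-2 assessment falls at its start.

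**Step 2: false positives at week 2.** The number of comparisons is 3 + 1 = 4.

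- Independent tests: 1 − 0.95^4 = 0.185.
- All four equally correlated at 0.3 to 0.7: about 17% to 13% by simulation.
- Pain sites correlated at 0.7, ROM independent: about 15% by simulation.
- Pain counted as one test: 1 − 0.95^2 = 0.0975.

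**Step 3: chance imbalance at week 2.** In SD units, the standard error of the difference is √(2/25) = 0.283, so differences up to 1.96 × 0.283 = 0.55 SD are within ordinary chance. Unadjusted tests at later visits leave that imbalance uncorrected.

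**Step 4: gain from using week 2 as a covariate.** Residual variance is multiplied by 1 − ρ², and the equivalent unadjusted arm size is 25/(1 − ρ²). The difference detectable with 80% power is (1.96 + 0.84) × √(2/25) × √(1 − ρ²), by normal approximation.

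| Assumed ρ | Variance factor | Equivalent n per arm | Detectable difference (SD) |
|---|---|---|---|
| 0 (no adjustment) | 1.00 | 25 | 0.79 |
| 0.3 | 0.91 | 27.5 | 0.76 |
| 0.5 | 0.75 | 33.3 | 0.69 |
| 0.6 | 0.64 | 39.1 | 0.63 |

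**Step 5: when adjustment is unsafe.** If knowledge of the allocation shifts the week-2 value by δ and the covariate slope is β, the adjusted later contrast moves by about −β × δ. With β = 0.5 and δ = 0.3 SD (both assumed), that is 0.5 × 0.3 = 0.15 SD. Week 2 is a clean baseline only if allocation is unknown until it has been recorded.

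**The case against.** Randomising after surgery is valid, and its stated purpose, avoiding bias during the operation, is met. Several premises are inferred. The interval from surgery to allocation is not given, and open-label status does not date disclosure. The trial group's care in weeks 0 to 2 is implied, and so is the order of assessment and first heel walking. The plan says week-2 values will be measured; it does not list a test for each time point. Reporting week 2 is legitimate as description, or as a check on open-label reporting. Week 2 supplies only 4 of 47 comparisons (9 radiographic, 15 pain, 5 ROM, 3 hallux score, 15 FAOS), so multiplicity is a general matter. Allocating in clinic, after staff have seen the foot, opens a route to selection when the protocol describes only a computer-generated number and no concealment.

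Most of this stands and limits the claim. A reader might infer that patients are allocated, and know it, exactly two weeks before the regimens diverge, that no regimen effect at week 2 is possible, or that the plan explicitly commits to testing week 2. These are natural readings, but none is written. A reader might also infer that week 2 should be the baseline covariate whatever the timing of allocation. That does not follow: the same open knowledge that makes week-2 differences hard to interpret would contaminate the covariate.

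What the objection does not remove is that the described contrast starts at the 2-week visit, the week-2 values are listed as outcomes, and the general analysis rule does not set them apart. The stated reason for late randomisation is met equally well at that visit.

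**Conclusion.** The point holds in a limited form. As written, week-2 pain and ROM come under unadjusted between-group tests although no regimen difference before that visit is described. A difference there would reflect chance or knowledge of allocation.

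The false-positive risk is at most about 18.5%, under independence, and nearer 13 to 17% at the correlations tried. The variance reduction of 9 to 36% rests wholly on assumed correlations of 0.3 to 0.6, and could be smaller for visits as late as week 26. Only pain and ROM benefit. The primary radiographs are taken at 12, 18 and 26 weeks and have no week-2 value, so the primary comparison is unaffected. The change is worth making because it uses a visit already scheduled.

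**What to change.** (a) Open a concealed allocation at the existing 2-week visit, after week-2 pain and ROM are recorded and before any heel walking. State the concealment method, when allocation is disclosed, the order of assessment and first heel walking, and whether care in weeks 0 to 2 is the same in both arms.

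(b) Label week-2 pain and ROM as descriptive, not as evidence of a regimen effect. With (a), or with allocation otherwise concealed until that assessment, use the week-2 value as the baseline covariate for the same measure at weeks 6 to 26. If allocation is already known before week 2, the value is post-randomisation: keep the adjusted model as a sensitivity analysis and state that limitation.

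**Cost.** (b) is analysis-plan wording. (a) moves allocation to a visit already in the schedule. Its downsides are that patients learn their regimen later and that allocation must be kept from clinic staff until the assessment is complete.

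### The radiological primary comparison is not adjusted for pre-operative deformity severity, which nothing else in the plan controls, at a cost in precision and in validity given the imbalance that occurs

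*Combined protocol and SAP*

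**What the plan says.** All of the following is in the combined protocol and SAP.

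- **Allocation** (Patients and Methods, Patients): "Parallel groups will be allocated at 1:1 ratio via a computer generated random number, with 25 patients at each group". No blocks, strata, minimisation or list type is described.
- **Timing** (same section): "Randomization will be performed after the end of the EDSTP surgery to ensure there is no bias during the surgical procedure". Anything measured before the operation therefore precedes allocation.
- **Entry** (same section): the target is 50 adults having the endoscopic procedure. The exclusions are disabilities that could impair adherence, and additional procedures. Neither concerns severity.
- **Primary outcome** (Study outcomes): "Radiological changes including hallux valgus angle (HVA), intermetatarsal angle (IMA), and tibial sesamoid position by weight bearing feet X-Rays will be measured at 12, 18,". The third and last film is at week 26. No pre-operative film is listed, and the reference point for a change is not given.
- **Analysis** (Statistical analysis): "Between-group comparisons will be conducted by one-way analysis of variance (continuous normal distributed data), Mann-Whitney U test (continuous non-normally distributed data), or chi-square test (categorical". No baseline value or other covariate appears. Tests are two-sided at 0.05.

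**The concern.** Severity could be controlled at entry, at allocation or in the analysis, and the plan does none of these. Pre-operative severity is a natural prognostic factor for the follow-up angles, because both measure the same deformity. If the early-walking arm happens to receive more of the severe feet, its follow-up angles may look worse for that reason alone. If it receives fewer, a real loss of correction may be masked. The plan hypothesises that early weight bearing leaves the correction as stable as the traditional regimen, and that statement will rest on one comparison of 50 patients. How that comparison behaves under the imbalance that actually occurs therefore matters, as well as its long-run average.

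**Working it through.** **The plan's own figure.** 25 + 25 = 50 at 1:1, which agrees. The documents give no SD, effect size, margin or power, so nothing further can be reproduced. The SD-scale inputs below are assumptions, shown over a range.

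**1. Chance of an uneven split.** Assume 25 of 50 feet are severe and a fixed 25/25 list is used. The number of severe feet in the early-walking arm is hypergeometric (50, 25, 25).
- P(15 or more) = Σ C(25,k)² / C(50,25), k = 15 to 25, = 0.129.
- P(16 or more) = 0.044.
- Counting either arm, these double to 0.258 and 0.089.

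**2. False-harm rate at exactly 15 v 10.** Let g be the severe-minus-mild gap at follow-up, in within-class SDs, with no treatment effect.
- Shift = g × (15/25 − 10/25) = 0.20g.
- The true SE given the split is √(2/25) = 0.283.
- The unadjusted test uses an SE inflated by the gap: 0.283 × √(1 + g² × 0.24 × 25/24).
- Rejection in the harm direction ≈ 1 − Φ[(1.96 × test SE − 0.20g) / 0.283].

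| g | Shift (SD) | Test SE | z | False-harm rate | Mirror split, 10 v 15 |
|---|---|---|---|---|---|
| 0.3 | 0.06 | 0.286 | 1.77 | 3.8% | 1.4% |
| 0.5 | 0.10 | 0.292 | 1.67 | 4.8% | 0.9% |
| 1.0 | 0.20 | 0.316 | 1.48 | 6.9% | 0.2% |

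The mirror column replaces −0.20g by +0.20g. Simulations of the same set-up agree, at about 3.6% to 3.8%, 4.6% to 4.8% and 6.7% to 6.9%. The nominal one-direction rate is 2.5%.

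**3. Average over all splits.** Weighting the conditional rates by the hypergeometric probabilities returns about 2.5% in the harm direction. A separate simulation (20,000 trials per scheme, continuous baseline, correlation 0.5) gave a two-sided error of 4.8% with independent draws and 4.9% with a fixed 25/25 list.

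**4. Severity as a continuous measure.** The baseline difference between arms has SE √(2/25) = 0.283 SD, so P(|difference| > 0.5 SD) = 0.077. For a baseline-outcome correlation ρ of 0.3, 0.5 or 0.7:
- A 0.5 SD imbalance shifts the post-operative comparison by ρ × 0.5 = 0.15, 0.25 or 0.35 SD. The two-sided error given that imbalance is 7.1%, 10.7% or 15.6%.
- At a 0.3 SD imbalance the error stays near nominal (4.4% to 5.1%), although the estimate still shifts by 0.09 to 0.21 SD.
- An unadjusted change from baseline does not remove the problem. At 0.5 SD the shift is (ρ − 1) × 0.5 = −0.35, −0.25 or −0.15 SD, in the opposite direction.

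**5. Gain from adjustment.** Adjusting for the baseline value multiplies the residual SD by √(1 − ρ²). Power at an assumed 0.8 SD effect = Φ[0.8 / (0.283 × √(1 − ρ²)) − 1.96].
- Unadjusted: Φ(2.83 − 1.96) = 80.7%.
- ρ = 0.3: Φ(2.97 − 1.96) = 84.3%.
- ρ = 0.5: Φ(3.27 − 1.96) = 90.4%.
- ρ = 0.7: Φ(3.96 − 1.96) = 97.7%.

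The difference detectable with 80% power falls from 0.79 SD to 0.76, 0.69 or 0.57 SD.

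**The case against.** The strongest reply is that randomisation already accounts for chance imbalance. Step 3 confirms this: the unadjusted test holds its level on average, and bad splits are offset by good ones. A reader might infer from the conditional rates that the planned test is biased towards finding harm. It is not. Those rates apply only once an unfavourable split has occurred, and the mirror split is equally likely.

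The size is also uncertain. The documents give neither the share of severe feet nor how far pre-operative severity persists after correction. With a gap of 0.3 SD the effect is modest. If a change means change from a reference film, the shift differs in size and direction. All of this stands. It limits the size of the point but does not answer the loss of precision, which adjustment recovers whatever split occurs.

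A reader might also infer that the allocation cannot deliver 25 per group. Independent 50:50 draws would give exactly 25/25 with probability C(50,25)/2⁵⁰ = 11%. But the plan does not say whether the sequence is simple or restricted, and a computer-shuffled list of 25 + 25 fits the sentence and meets its final clause. Even under independent draws, unequal sizes cause no bias, and a 20:30 split keeps 4 × 20 × 30 / 50² = 96% of the information. Equal group sizes would not balance severity in any case.

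**Conclusion.** The point holds as a low-priority improvement to the analysis. Pre-operative severity is not limited at entry, not described as a stratification factor and not in the primary comparison, although the outcome is the deformity itself. The consequence is lost precision, and an estimate that can be pushed either way by the imbalance seen. It is not an inflated overall error rate. The conditional error figures rest on half the feet being severe, a fixed 25/25 list and a gap of 0.3 to 1 SD. The power figures rest on a 0.8 SD effect and correlations of 0.3 to 0.7. None of these inputs is in the documents.

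**What to change.** In Statistical analysis, replace the unadjusted test of the primary outcome with a linear model (ANCOVA) of each follow-up HVA and IMA on arm and the pre-operative value of the same angle. For tibial sesamoid position, also include pre-operative severity in the comparison. In Study outcomes, list the pre-operative weight-bearing film as a recorded measurement.

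Stratifying the allocation by pre-operative HVA is optional once the analysis adjusts, and would not directly balance IMA or sesamoid position. If it is done, fix the cut-point before the first patient and include the stratum in the model.

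The cost is one covariate per model and the recording of the pre-operative film. That film is assumed to be routine; if it is, patients carry no added burden. If it is not, it would have to be added before surgery.
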